In order to provide an overview of the efficacy and safety of the lidocaine 5% medicated plaster in treating LNP, Mick et al. reviewed 60 clinical studies, as well as case reports and pharmacological studies. 10 Most are related to PHN, PDN or post-surgical/posttraumatic/scar pain, but other LNP conditions are also included, such as idiopathic sensory polyneuropathy, complex regional pain syndrome and carpal tunnel syndrome sequelae. In the majority of studies, the lidocaine plaster was added to the existing analgesic regimen. The plaster was found to be efficacious in both short-term and longterm controlled, randomised or open-label studies. Patients' quality of life (QoL) markedly improved in a variety of NP conditions and pain relief was sustained over long-term treatment. The plaster was very well tolerated, the most common adverse drug reactions (ADRs) being mild to moderate application site reactions. A later reappraisal of the clinical evidence for using the lidocaine 5% medicated plaster retrieved all relevant efficacy and safety studies from a literature search up to September 2015.²³ Analysis suggested that the lidocaine plaster is an effective and well-tolerated treatment option in patients with LNP. It was found to be easy to use, to improve patients' QoL, to have an excellent tolerability profile and to be associated with both a lack of systemic ADRs and a low potential for drug-drug interactions. Furthermore, its safety profile and ease of use can significantly increase patients' adherence to chronic treatment, with consequent benefits on efficacy and rehabilitation. Taking a wider perspective, a number of studies have recorded significantly better QoL scores following commencement of treatment with the lidocaine plaster.²⁴ Allodynia is often a prominent feature of LNP, and is usually considered to be one of the most distressing and debilitating symptoms of NP.^{25,26} Therefore, one contributory factor to the improved QoL scores is likely the reduction in the area of allodynia – typically > 50% - produced by treatment with the lidocaine plaster. 27,28 Reducing the painful area, which can increase tolerance of bathing and contact with clothing, is therefore a justifiable treatment goal for this medication.

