3.2 Secondary objectives

- To compare the quality of life profiles over the 24 weeks' treatment period between the treatment arms.
- To compare the effectiveness in terms of pain relief between the treatment arms.
- To compare the effectiveness in different aspects of quality of life (sleep, mood) between the treatment arms.
- To compare the drug tolerance between systemic and topical treatment.
- To identify the difference between topical and systemic treatment in terms of functional status of the patient.

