3.5 Secondary endpoints

- Long term quality of life profile;
- Reduction in pain intensity (PI-NRS);
- Time to worsening of the pain and use of rescue medication for pain (MQS III-R);
- Global perceived effect (GPE);
- Effect on mood (Hospital Anxiety and Depression Scale);
- Quality of sleep (NRS and ISI);
- Percentage of patients without systemic drug related side effects (dizziness, fatigue, vertigo, somnolence, headache, blurred vision);
- Time to discontinuation of the study drug and proportion of patients stopping the drug;
- Participation in activities (Utrecht Work Engagement Scale-9);
- Impact of pain on functioning (interference BPI);
- Work Productivity and Activity Impairment (WPAI: Neuropathic Pain, v2.2, Belgium);
- Neuropathic Pain Symptom Inventory (NPSI).

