7.4 Blinding

No blinding is necessary for this open label trial.

Blinded assessment for the 3 treatment arms seems impossible in this case considering the clear difference in treatment modalities for the three therapeutic regimens. There is only one systemic treatment, versus two topical treatment solutions. In addition, the two topical treatment strategies differ significantly from each other (daily application versus three-monthly application, no skin reaction compared to neurogenic inflammation during a couple of hours after application of capsaicin). As such trial participants, pharmacists and care providers are unblinded to intervention groups.

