7.7 Trial assessments

The study comprises a screening period of maximum 21 days, randomisation (d-21 to d-1), a baseline visit at day 0 (start of treatment), a treatment period of 24 weeks and a post-treatment period of 2 weeks (24-26 weeks). Considering the pragmatic nature of the proposed trial clinic visits are kept to an absolute minimum.

The **clinical visits** take place at day 0 (V1), week 4 (V2), 12 (V3), 18 (V4), 24 (V5) and 26 (V6) which is comparable to a schedule which would be maintained in routine clinical care. A deviation of +/- 5 days is allowed for the clinical visits. The assessments made at these visits are (*routine care assessments are indicated in bold):*

- Documentation of the study intervention: number of patches (lidocaine and capsaicin), location, dosage used (pregabalin and gabapentin), compliance and discontinuation check
- Documentation of size of painful area
- Assessment of adverse events
- Assessment of systemic drug related side effects (e.g. dizziness, fatigue, vertigo, somnolence, headache, blurred vision) (not on baseline visit)

- · Concomitant medication use
- Only during V2 and V4 clinical sensory testing will be repeated (using the Boston Bedside Quantitative Sensory Testing Battery)

The majority of the assessments (patient reported outcomes and experiences) will be performed by making use of an online platform, enabling patients to complete the different assessments themselves without having to schedule a clinic visit. The use of the online platform will significantly reduce the work load for the patients involved in this study. Per regular weekly online assessment, the required time investment will not exceed 15 minutes. The online assessments on a monthly basis (n = 7 in total) will never require more than 30 minutes (which can be split over different moments).

Online assessments: weekly basis

A deviation of max. 48 hours is allowed for the completion The following procedures and assessments will be carried out:

- Assessment of reduction in pain intensity using PI-NRS
- Assessment of analgesic medication use (using MQS III)
- Quality of sleep: Sleep NRS
- Assessment of systemic drug related side effects (not collected at baseline)
- Discontinuation of study drug (not collected at baseline)
- Participation in activities: Utrecht Work Engagement Scale-9

Online assessments: monthly basis (baseline, week 6, 10, 14, 18, 22)

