All SAEs assigned by the PI or delegate (or following central review) as both suspected to be related to IMP-treatment and unexpected will be classified as SUSARs and will be subject to expedited reporting to the Federal agency for medicines and health products (FAMHP). The Sponsor will inform the FAMHP (through notification of the occurred SUSAR using the EudraVigilance system), the EC and the Marketing Authorisation Holder of SUSARs within the required expedited reporting timescales. EudraVigilance supports

the electronic transmission of ICSRs between electronic data interchange (EDI) partners: EMA, national competent authorities (NCAs), marketing authorisation holders (MAHs) and sponsors of clinical trials in the European Economic Area (EEA).

See the following table to see who needs to report what according to European guidelines.

Who	What	Reference
Sponsors of clinical trials Marketing authorisation holders National competent authorities	Reports of suspected unexpected serious adverse reactions (SUSARs) via safety reports (ICSRs/acknowledgements)	Directive 2001/20/EC Detailed guidance on the collection, verification and presentation of adverse event/reaction reports arising from clinical trials on medicinal products for human use (CT-3)
Sponsors of clinical trials Marketing authorisation holders	Information on investigational medicinal products via product reports (XEVPRMs/acknowledgeme nts)	Detailed guidance on the collection, verification and presentation of adverse event/reaction reports arising from clinical trials on medicinal products for human use (CT-3)

The point where recording / reporting starts in this study protocol will be:

- For SAEs consent
- For ARs / SARs and SUSARs administration of the 1st IMP dose

In the case of our low interventional trial with an IMP that has an extensively documented safety profile, only those non-serious ARs that the investigator considers important will be captured, such as sedation, skin irritation, development of blisters on the skin. Pharmacovigilance reporting will occur according to the requirements from FAMHP for medication with a marketing authorisation.

Safety reporting periods for SAEs and SARs (30 days after the last study visit) are equal across all arms of a randomised trial to prevent any bias in reporting.

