"Severe" is often used to describe intensity of a specific event, which may be of relatively minor medical significance. "Seriousness" is the regulatory definition supplied above.

Operational definitions for (S)AEs

In the OpenClinica eCRF system, (S)AE forms will be designed and made available to all participating sites. Data extraction from OpenClinica can be restricted to only include the reported (S)AEs. Participating sites will need to report SAEs to the Sponsor via mail within 24 hours of awareness and AEs through OpenClinica within 10 days of awareness.

In all cases AEs and / or laboratory abnormalities that are critical to the safety evaluation of the participant must be reported to the Sponsor; these may be volunteered by the participant, discovered by the investigator questioning or detected through physical examination, laboratory test or other investigation. Where certain AEs are not required to be reported to the Sponsor, these should still be recorded in the participant's medical records. Clear guidance in the protocol should state where this is the case (see appendix 3 for further details).

[figure not shown]
Since all IMPs being used are licensed, the latest SmPC will be used in this protocol.

The IMP reference documentation that is used for pharmacovigilance purposes is used to assess the causality and expectedness of events and will be checked by the Sponsor for changes on the anniversary of the Clinical Trial Authorisation. A statement will be included in the protocol describing which document is approved for use within the trial for pharmacovigilance monitoring (most current SmPC of the different IMP's used in this trial).

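### The side-effect endpoint for tolerance counts only systemic symptoms, so on its own it favours the topical arms and cannot register application-site reactions

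*Protocol*

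**What the plan says.** Protocol section 3.2 sets the objective: "To compare the drug tolerance between systemic and topical treatment". Two secondary endpoints in section 3.5 serve it, and the trial summary pairs them under the same objective.

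- Side effects: "Percentage of patients without systemic drug related side effects (dizziness, fatigue, vertigo, somnolence, headache, blurred vision".
- Discontinuation: "Time to discontinuation of the study drug and proportion of patients stopping the drug".

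Section 7.7 puts the first on the weekly online questionnaire in every arm: "Assessment of systemic drug related side effects (not collected at baseline". The same systemic assessment recurs at clinic visits V2 to V6. Section 10.3.3 compares the percentage with systemic effects at 6 and 26 weeks by chi-square or Fisher's exact test, and over time with a generalised linear mixed model.

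On the patches, section 1 says of the lidocaine plaster that it was well tolerated, "the most common adverse drug reactions (ADRs) being mild to moderate application site reactions". Section 7.4 mentions "neurogenic inflammation during a couple of hours after application of capsaicin". Section 2 expects topical patients to avoid systemic effects.

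For other non-serious reactions, section 9.1 states that "only those non-serious ARs that the investigator considers important will be captured". It goes on to give sedation, skin irritation and blister formation as examples. Adverse events are assessed at all visits V1 to V6 in all arms (sections 7.7 and 7.8). Appendix 2 requires sites to report "AEs through OpenClinica within 10 days of awareness".

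**The concern.** The objective is tolerance of each route of treatment, but the side-effect endpoint looks only for the kind of harm the protocol associates with the systemic arm. A patient with a week of burning and blistering under a plaster, and no systemic symptom, counts as a success on this endpoint. A pregabalin patient with a mild drug-related headache counts as a failure. If the percentage is read as a statement about tolerance in general, part of any advantage for topical treatment comes from what was asked.

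The same gap affects capsaicin versus lidocaine, which section 3.1 lists among the three comparisons of interest. The harms typical of both products are local, and this endpoint is silent on them. Local events that do reach the database depend on a threshold set by an investigator who knows the treatment and may differ between sites, so their rates compare poorly between arms.

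**Working it through.** **1. The plan's own figures.** The protocol gives no figure for the tolerance comparison. Its sample size for the primary endpoint (section 10.1) reproduces:

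- Inputs: difference 0.08, SD 0.240, two-sided alpha 0.05/2 = 0.025, power 80%.
- Normal approximation: n = 2 × (2.2414 + 0.8416)² × (0.240/0.08)² = 2 × 9.505 × 9 = 171.1, so 172. The two-sample t-test gives 172.35, so 173 as stated.
- With 12% drop-out: 173/0.88 = 196.6, so 197 per arm, and 3 × 197 = 591.
- Patients on a topical product: 2 × 197 = 394 of 591, two-thirds.

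Nothing in this point changes these numbers.

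**2. Which route captures which harm.**

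| Route | Systemic symptoms | Application-site reactions |
|---|---|---|
| Weekly online form, about 26 times | asked | no item stated |
| Systemic side-effect assessment, V2–V6 | asked | no item stated |
| General adverse-event assessment, V1–V6 | yes | yes |
| Non-serious reaction entry (9.1) | if judged important; sedation named | if judged important; skin irritation and blisters named |
| Side-effect endpoint and its tests (3.5, 10.3.3) | counted | not counted |
| Discontinuation endpoint (3.5, 10.3.3) | counts if the drug is stopped | counts if the drug is stopped |

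The asymmetry sits in the first, second and fifth rows. The other three treat both kinds of harm alike.

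**3. What the asymmetry could do.** The protocol gives no rates for these reactions, so the rates here are assumptions. Suppose a share h of pregabalin patients has a systemic reaction, the same share h of patients on one patch has a local reaction, and a background share b of the patch patients reports a listed systemic symptom. Harm on the patch is then at least h. The endpoint shows 1 − h free on pregabalin and 1 − b on the patch.

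For n = 173 per arm and two-sided alpha 0.05, the chance of a significant difference is

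Φ{ [ |h − b| − 1.96 × √(2p̄(1 − p̄)/n) ] / √( [h(1 − h) + b(1 − b)]/n ) }, with p̄ = (h + b)/2.

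Worked case h = 0.30, b = 0.15: p̄ = 0.225; √(2 × 0.225 × 0.775/173) = 0.0449; √((0.21 + 0.1275)/173) = 0.0442; (0.15 − 1.96 × 0.0449)/0.0442 = 1.40; Φ = 0.92.

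| h | b | Free on pregabalin | Free on patch | Chance of p < 0.05 |
|---|---|---|---|---|
| 0.30 | 0.05 | 70% | 95% | >99% |
| 0.30 | 0.10 | 70% | 90% | >99% |
| 0.30 | 0.15 | 70% | 85% | 92% |
| 0.20 | 0.05 | 80% | 95% | 99% |
| 0.20 | 0.10 | 80% | 90% | 74% |
| 0.20 | 0.15 | 80% | 85% | 23% |

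An endpoint counting either kind of harm would, for h = 0.30, show 70% free on pregabalin (assuming no local reactions there). On the patch it would show between 70% (local and systemic fall in the same patients) and 1 − 0.30 − 0.15 = 55% (no overlap, b = 0.15). The apparent advantage disappears or reverses.

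**4. The recording rules.** Section 9.1 limits entry of non-serious reactions to those judged important. The Appendix 2 reporting sentence carries no such limit. Appendix 2 does foresee that some events need not go to the sponsor, asks for clear guidance on which, and refers to Appendix 3, whose chart is not shown. Section 9.1 supplies only discretion. The two texts are not aligned on which non-serious events are entered.

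**The case against.** The defence has substance. A reader who stops at the filter in section 9.1 might infer that patch reactions go unrecorded. The text does not support that: two of its three examples are skin reactions, and the filter applies to every arm, sedation included. Nor is it fair to set some 31 enquiries about systemic symptoms (26 weekly plus 5 visits) against none for local ones. Adverse events are assessed at every visit in all arms, and capsaicin is applied in hospital under supervision.

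A reader might also infer that the whole tolerance comparison favours topical treatment by design. It does not. Discontinuation is a second tolerance endpoint, collected weekly in all arms, and a patient who stops because of skin reactions counts against the patch. The systemic endpoint is openly labelled as systemic, and all arms answer the same questions.

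Other supposed contradictions fall away. Section 9.2 asks for recording in line with the protocol's requirements and so defers to section 9.1. Assessing events at a visit is compatible with a rule on which of them are entered. The questionnaire items are not reproduced, section 7.7 gives its visit list by way of example, and section 11.3.1 describes the platform's side-effect field in general terms. One can therefore say only that no local item is stated. Tabulation of local events by arm may also be in an analysis plan not shown here.

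What remains is narrower. Systemic symptoms have a structured patient-reported route that bypasses the filter; local reactions have no stated equivalent and no planned comparison. A capsaicin reaction lasting hours may rest on recall by the week 4 visit if it was not entered on the application day. Discontinuation only partly fills the gap. With capsaicin repeatable every 90 days, there is normally no second application to decline before the 6-week (42-day) comparison. Section 7.11 also allows a switch for insufficient pain relief, so the measure mixes efficacy with tolerance.

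**Conclusion.** The concern holds for the side-effect endpoint, not for the tolerance objective as a whole and not as a claim that local harms are left out of the trial. The systemic-only percentage cannot register the reactions the protocol names as typical of the topical products. Alone it favours the topical arms, and it does not inform capsaicin versus lidocaine on local harm. Capture of local reactions rests on general enquiry at visits and on the judgement of an unblinded investigator.

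The size cannot be estimated from the protocol. Under the assumed rates, the spurious gap ranges from 5 to 25 percentage points, with a 23% to over 99% chance of significance at 173 per arm. This affects a secondary objective only. The correction is worth making because transient local reactions not asked about during follow-up cannot be reliably recovered at analysis.

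**What to change.** - Add application-site reactions (pain or burning, redness, itching, blistering; yes/no and intensity) to the existing weekly side-effect questionnaire and to the V2–V6 list, in all arms.
- Report the percentage of patients without any solicited side effect, systemic or local, beside the systemic-only percentage. Label the latter as systemic tolerability, and base any tolerance conclusion on both together with discontinuation.
- Reconcile section 9.1 with Appendix 2 in one rule on which non-serious events are entered in the eCRF, identical in all arms.

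The cost is one amendment, a few more questionnaire items and some extra adverse-event entries. The topical profile may look less favourable as a result.

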9.2 Responsibilities

Principal Investigator (PI):

Checking for AEs and ARs when participants attend for treatment / follow-up.

- 1. Using medical judgement in assigning seriousness, causality and expectedness by using the Reference Safety Information approved for the trial.
- 2. Ensuring that all SAEs and SARs (including SUSARs) are recorded and reported to the Sponsor within 24 hours of becoming aware of the event and provide further follow-up information as soon as available.
- 3. Ensuring that AEs and ARs are recorded and reported to the Sponsor in line with the requirements of the protocol.

Chief Investigator (CI) or delegate:

- 1. Clinical oversight of the safety of patients participating in the trial, including an ongoing review of the risk / benefit.
- 2. Using medical judgement in assigning seriousness, causality and expectedness of SAEs where it has not been possible to obtain local medical assessment.
- 3. Immediate review of all SUSARs.
- 4. Review of specific SAEs and SARs in accordance with the trial risk assessment and protocol as detailed in the Trial Monitoring Plan.
- 5. Assigning Medical Dictionary for Regulatory Activities (MedDRA) or Body System coding to all SAEs and SARs.
- 6. Preparing the clinical sections and final sign off of the Development Safety Update Report (DSUR).

Sponsor:

- 1. Central data collection and verification of specific ARs, all SAEs, SARs and SUSARs according to the trial protocol onto a safety database.
- 2. Reporting safety information to the CI, delegate or independent clinical reviewer for the ongoing assessment of the risk / benefit according to the Trial Monitoring Plan.
- 3. Reporting safety information to the independent oversight committee identified for the trial (Trial Steering Committee (TSC)) according to the Trial Monitoring Plan.
- 4. Expedited reporting of SUSARs to the Competent Authority (FAMHP IN BE) and EC within required timelines.
- 5. Notifying Investigators of SUSARs that occur within the trial.
- 6. Checking for (annually) and notifying PIs of updates to the Reference Safety Information for the trial.
- 7. Preparing standard tables and other relevant information for the DSUR in

collaboration with the CI and ensuring timely submission to the FAMHP and REC.

Trial Steering Committee (TSC):

In accordance with the Trial Terms of Reference for the TSC, they will periodically review safety data. The role of the TSC is to provide overall supervision for the trial and provide advice through its Chair. The ultimate decision for the continuation of the trial lies with the TSC.

In preparation of the meeting of the Trial Steering Committee a physician, independent to the trial, will assess the causality of the adverse events and reports his/her findings to the TSC.

Trial Management Group (TMG):

The TMG is responsible for the day-to-day running and management of the trial. It holds regular teleconferences and face-to-face meetings.

9.3 Notification of deaths

All deaths, from written informed consent till 14 days post cessation of trial treatment must be recorded on SAE form and mailed to sponsor of the trial within 24 hours of awareness after the patient has passed away. Also deaths deemed unrelated to the IMP, if they occur earlier than expected will be reported to the sponsor

9.4 Reporting urgent safety measures

If any urgent safety measures are taken, the CI/Sponsor shall immediately and in any event no later than 3 days from the date the measures are taken, provide electronic notice to EudraVigilance (fully automated safety and message-processing mechanism using XML-based messaging) and the relevant EC of the measures taken and the circumstances giving rise to those measures.

